6.4 SUBJECT SETS ANALYSED

The following analysis sets will be defined for statistical analyses:

Enrolled Set (ES):

This patient set includes all patients who signed informed consent. The ES will be used for the analyses of patient disposition.

Randomized Set (RS):

This patient set includes all patients who were randomized in the trial. Treatment assignment will be as randomised. It will be used for analyses of subject for baseline demographics, disease characteristics and iPD etc.

Full Analysis Set (FAS):

Date: 07-08-2024, Version 1.0

This patient set includes all randomized patients and received at least one dose of study drug. This is the main analysis set for presentation of efficacy data. Patients will be analysed according to their planned treatment group.

• Full Analysis Set (FAS-Post16):

This patient set includes all randomized patients and received at least one dose of study drug during the maintenance period III (from Week 16 to set for presentation of efficacy data post week 16.

Proprietary confidential information © 2024 Boehringer Ingelheim International GmbH or one or more of its affiliated companies.

Safety Analysis Set (SAF):

1368-0098

This subject set includes all subjects who were randomized and received at least one dose of study drug. This is the main analysis set for safety. Subjects will be analysed according to the actual treatment received at Day 1.

Per-Protocol Set (PPS):

This subject set includes all subjects in the randomized set who adhered to the CTP without any iPDs which are flagged for exclusion from the PPS. The PPS will be used for sensitivity analysis on the primary endpoint.

The discussion of all exceptional cases and problems and the decisions on the allocation of patients to populations will be made at latest at the DBLM. A separate DBLM will be performed prior to each database snapshot of this trial.

PK Parameter Analysis Set (PKS) (if applicable):

This patient set includes all patients in the RS who provide at least one evaluable observation for the Spesolimab concentration, which was not flagged for exclusion. The PKS will be used for the display of concentrations.

ADA Analysis Set:

Date: 07-08-2024, Version 1.0

This patient set includes all patients in the RS who provide baseline and at least one reportable post-baseline ADA data.

Biomarker Set (BMS) (if applicable):

This patient set includes all patients in the RS who have analyzable data (observed or imputed) in at least one biomarker.

Handling of Treatment Misallocations in Analysis Sets

If a subject is treated but not randomized, they will be excluded from the efficacy analysis and safety analysis by definition. However, subjects under such circumstances will be described in the final clinical trial report.

If a subject is randomized but takes incorrect treatment during the study, then:

- For efficacy analyses according to RS and PPS, they will be reported under their randomized treatment groups.
 - O In the case of stratification error at randomization, the subjects will be analyzed according to the stratum to which they actually belong to (regardless of any mis-assignment to treatment based on identification of the wrong stratum from IRT), as such an error occurs before randomization and is therefore consistent with regulatory guidance.
- For the safety analysis based on SAF, the actual treatment will be used as below:

Proprietary confidential information © 2024 Boehringer Ingelheim International GmbH or one or more of its affiliated companies.

- o If a subject is planned to receive administration of Spesolimab (randomized to Speso) at day 1, then patients will be reported under their randomized treatment group for safety analysis because the overall safety profile is expected to be driven by the amount of Spesolimab received in totality over the entire treatment duration. It is not expected that the safety profile will deviate from the planned treatment regimen if the subject receives only a few vials of the incorrect medication at only some dosing occasions.
- o If a subject is planned to receive placebo treatment at day 1, then they will be reported under the placebo arm if they are treated and receive no vial of randomized Spesolimab. If the subject receives >= 1 vial of randomized Spesolimab before week 16, then the patient will be handled differently for efficacy analysis and safety analysis. It will keep as placebo for efficacy reporting. For safety, then the patients will be reported as their treated Spesolimab group.

Table 6.4: 1 Subject sets analyzed

Subject Set								
Class of endpoint	ES	RS	FAS	SAF	PPS	PKS	ADA	BMS
Disposition	X							
Demographic and baseline characteristics			X					
Baseline condition / Medical history			X					
Compliance and Exposure				X				
Concomitant medication/therapy			X					
iPD		X						
Primary endpoint			Xª		X^b			
Secondary endpoints			X					
Further endpoints			Xc					
Safety endpoints				X				
Concentration (if applicable)						X		
Anti-drug antibody							X	
Biomarker (if applicable)								X

a Primary analysis; b Sensitivity analysis; c FAS including FAS-post 16.

Date: 07-08-2024, Version 1.0

Proprietary confidential information © 2024 Boehringer Ingelheim International GmbH or one or more of its affiliated companies.

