From Visit 14 , there is an option of increasing the dose to the maximum subcutaneous dose of applied to low dose treatment group participants only, via IRT in a blinded manner) if they have compared to baseline and the investigator agrees with the dose increase.
For trial participants initially randomised to placebo group, from Visit 10 to Visit 13 (both inclusive), the participants will be administered a matching placebo Visit 14 to Visit 31 (both inclusive), the participants will be dose of spesolimab
From Visit 23 on, trial participants will continue to receive the assigned dosing regimen, at least until the results of are available. Upon availability of the Phase IIb (Part 1) primary analysis efficacy and safety results, the dosing regimen may be adapted from Visit 23. For more detailed drug assignment and administration of doses for each trial participant, please see Section 4.1.5.
Follow-up phase and end of study  Trial participants completing EoT visit of the study may roll over to an if they agree and meet the eligibility criteria. These trial participants are not required to complete a safety follow-up period, and their EoT visit will be considered also their end of study (EoS) visit, which is the
Trial participants, who permanently discontinue trial drug earlier than Visit 31 do not qualify to enter the LTE trial for any other reason, will be invited to do the EoT visit instead of the next planned visit and will then enter a safety follow-up period

BI Trial No.: 1368-0098

c40061625-02 Clinical Trial Protocol Page 48 of 177

Proprietary confidential information © 2023 Boehringer Ingelheim International GmbH or one or more of its affiliated companies

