#### 7.2.6 Safety analyses

Adverse events will be coded using the Medical Dictionary for Drug Regulatory Activities (MedDRA). Standard BI summary tables and listings will be produced. All adverse events with an onset between start of treatment and end of the REP, a period of 16 weeks after the last dose of trial medication, will be assigned to the on-treatment period for evaluation.

The safety analysis will be performed by treatment at onset.

Safety analyses will be based on the TS. In general, safety analyses will be descriptive in nature and will be based on BI standards. No hypothesis testing is planned.

Statistical analysis and reporting of adverse events will concentrate on treatment-emergent adverse events, i.e. all adverse events occurring between start of treatment and end of the REP. Adverse events that start before first drug intake and deteriorate under treatment will also be considered as 'treatment-emergent'. Adverse events will be summarized by treatment at onset, and the treatment at onset of AE for the drug-related AE.

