6. GENERAL ANALYSIS DEFINITIONS

6.1 TREATMENT(S)

Part 1 (Phase IIb)

Date: 07-08-2024, Version 1.0

The analysis periods are defined relative to the day of randomization (Day 1) in Table 6.1:1:

Table 6.1: 1 Flow chart of analysis periods of the study according to randomized treatment

Study analysis period	Description	Start (included)	End (included)
Screening period	Screening	Earliest of (Date of informed consent, first screening procedure)	Date/time of start of the first study dose minus 1 minute.
Loading period (from Day 1 to	On- treatment period	Date/time of start of the first study loading dose (Day 1)	Earliest of i) Date/time of start of the first maintenance dose minus1 minute; ii) Date of end of last loading dose + 112 days at 11:59 p.m. if patient early discontinued study treatment before visit; iii) last contact date on End of Study page at 11:59 p.m.
Maintenance period I (from to Week 8)		Date/time of start of the first maintenance dose for visit (if applicable)	Earliest of i) Date/time of start of the study maintenance dose for Week 8 visit minus 1minute; ii) Date of end of last maintenance dose + 112 days at 11:59 p.m. if patient early discontinued study treatment before Week 8 visit; iii) last contact date on End of Study page at 11:59 p.m.
Maintenance period II (from Week 8 to Week 16)		Date/time of start of the study maintenance dose for Week 8 visit (if applicable)	Earliest of i) Date/time of start of the study maintenance dose for Week 16 visit minus 1minute; ii) Date of end of last maintenance dose + 112 days at 11:59 p.m. if patient early discontinued study treatment before Week 16 visit; iii) last contact date on End of Study page at 11:59 p.m.
Maintenance period III (from Week 16 to		Date/time of start of the study maintenance dose for Week 16 visit (if applicable)	Earliest of i) Date/time of the first treatment in OLE trial 1368.0130 minus1 minute if subject is rolled over; ii) Date of end of last maintenance dose + 112 days at 11:59 p.m. if patient early discontinued study treatment; iii) last contact date on End of Study page at 11:59 p.m.
Off-treatment phase ¹ (if applicable)	Off- treatment period	Date of end of last study dose + 113 days at 0:00 a.m.	Latest of i) Date of EOS visit; ii) last contact date on End of Study page at 11:59 p.m.

Proprietary confidential information © 2024 Boehringer Ingelheim International GmbH or one or more of its affiliated companies.

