Dates are defined individually per patient. If more than one date is associated with a specific visit, measurements associated with a specific date are assigned to a study analysis period according to the rules specified in the table. An analysis period will not extend beyond the start date of the following phase.

¹ The off-treatment period only exists for patients who early discontinued study treatment or choose not to enter the extension study 1368-0130, whose last contact date is after the date of end of last study treatment + 112 days.

The following labels for the treatment groups for all analysis is according to the randomized treatment up to Visit 14 (Week 16):

•	receive placebo);
•	"Speso Low" (
	[Week 16]);
•	"Speso Medium"
	[Week 16]);
•	
	[Week 16]):

- "Speso Total" (i.e. randomised to any of the spesolimab group);
- "Overall Total" (i.e. randomised to any treatment group regardless of placebo or Spesolimab group).

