7.8.1 Adverse Events

Date: 07-08-2024, Version 1.0

Unless otherwise specified, the analyses of AEs will be descriptive in nature, which will include all on-treatment events up to week 8, week 16 treatment, as well as all events during the whole on-treatment period respectively. All analyses of AEs will be based on the number of subjects with AEs and NOT on the number of AEs.

AEs will be coded with the most recent version of MedDRA®. Patients will be analyzed according to the actual treatment received.

The analysis of AEs will be based on the concept of treatment emergent adverse events (TEAE). That means that all AEs occurring between first drug intake till 112 days after last drug intake will be assigned to the on-treatment period. All AEs occurring before first drug intake will be assigned to 'screening' and all AEs occurring after last drug intake + 112 days will be assigned to 'follow-up' (for listings only). For details on the treatment definition, see Table 6.1:1.

The exposure adjusted incidence rate (per 100 patient years) of a selected treatment emergent adverse event is defined as the number of patients experiencing the adverse event per

Proprietary confidential information © 2024 Boehringer Ingelheim International GmbH or one or more of its affiliated companies.

treatment group during time at risk divided by the total time of patients at risk in that treatment group to contribute the event to the analysis multiplied by 100 (per 100 patient years).

Time at risk [patient years] = (date of onset of AE– first treatment start date within that treatment period + 1) / 365.25

If, for a patient, the selected treatment emergent adverse event didn't occur during the above defined treatment period (per Table 6.1:1) then the time at risk will be censored at the earliest of date of death, last contact date per EoS page, or the end of the above defined treatment period.

For each selected treatment emergent AE, the exposure adjusted incidence rate will be calculated as:

Incidence rate [1/100 Patient years (pt-yrs)] = 100 * number of patients with TEAE / Total TEAE-specific time at risk [patient years].

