7.8.2 Laboratory data

Date: 07-08-2024, Version 1.0

The analyses of laboratory data will be descriptive in nature and will be based on BI standards (9.3). The up to Week 16 and overall on-treatment period for laboratory analyses will be provided. Note that data from the central laboratory will be used for all displays described below, unless otherwise specified.

For continuous safety laboratory parameters, normalized values will be derived.

Normalization means transformation to a standard unit and to a standard reference range. The process of normalization, handling of repeat values at the same visit for by-visit displays, as well as standard analyses for safety laboratory data are described in the BI guidance for the Display and Analysis of Laboratory Data. All analyses considering multiple times of the ULN (as described below) will be based on standardized and not normalized values. For continuous

Page 42 of 64

c43421787-01

Proprietary confidential information © 2024 Boehringer Ingelheim International GmbH or one or more of its affiliated companies.

safety laboratory parameters, differences to baseline will be calculated. For all outputs, the last assessment before the first treatment at Day 1 is chosen as the baseline value.

Only patients with at least one available post-baseline value will be included in the analysis of an individual laboratory parameter. All individual laboratory data will be listed. Values outside the reference range will be flagged.

For derivation of the last value, the minimum value, and the maximum value, all values during the on-treatment period will be considered. These will be derived for analysis of laboratory, vital signs and local tolerability data. For identification of potentially clinically significant abnormal laboratory values, all values during on-treatment period will also be considered.

Descriptive statistics of laboratory values over time and for the difference from baseline ontreatment will be based upon normalized values, including summaries of the last value on treatment, the minimum value on treatment and the maximum value on treatment and corresponding change from baseline. Graphical displays via box plots/line plots will be produced for the last value, minimum and maximum value on treatment for each continuous laboratory endpoint.

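### Safety tables that run past Week 16 keep the Day 1 treatment group, so spesolimab events in switched placebo participants count under placebo, although the protocol requires treatment at onset

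*SAP*

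**What the plan says.** **Protocol.** Section 7.2.6 says "The safety analysis will be performed by treatment at onset" and repeats the rule for the AE summaries. Section 7.2.1 defines the Safety Analysis Set by actual treatment received, with no Day 1 limit. Section 3.1 moves the Part 1 placebo group to active drug: "Visit 14 to Visit 31 (both inclusive), the participants will be dose of spesolimab" (the gap is redaction). Table 1.4.2: 1 confirms the switch at Visit 14.

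**SAP.** Section 6.4 narrows the Safety Analysis Set rule: "Subjects will be analysed according to the actual treatment received at Day 1". Section 6.1 states that the "labels for the treatment groups for all analysis is according to the randomized treatment up to Visit 14 (Week 16" and defines the total-spesolimab group as "i.e. randomised to any of the spesolimab group". In Table 6.1: 1, Maintenance period III begins at "Date/time of start of the study maintenance dose for Week 16 visit (if applicable" and belongs to the on-treatment period.

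Several outputs cross the switch. AE analyses cover "all on-treatment events up to week 8, week 16 treatment, as well as all events during the whole on-treatment period respectively" (Section 7.8.1). For laboratory data, "The up to Week 16 and overall on-treatment period for laboratory analyses will be provided" (Section 7.8.2). Vital signs (7.8.3) and local tolerability (7.8.5) use the on-treatment period and state no Week 16 cut.

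SAP Section 4 undertakes to perform the protocol's analyses as planned apart from listed adaptations. The list concerns efficacy endpoints and does not mention safety grouping.

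**The concern.** From Week 16 every placebo participant still on treatment receives spesolimab, but the SAP's rule leaves that participant in the placebo column. Two errors follow in any pooled whole-period table. Events on spesolimab raise the placebo incidence, and spesolimab events and exposure are missing from the total-spesolimab column. Both make the drug look closer to placebo, most of all for harms that appear late or accumulate with exposure.

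This matters most in the final report, where the whole-period tables and exposure-adjusted rates will be read. Protocol Section 1.4.2 describes safety knowledge for this drug class as limited, so losing part of the spesolimab experience has a cost. There is no concurrent placebo group after Week 16. The correction therefore gives correct attribution, not a long-term randomised comparison.

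**Working it through.** **1. Does any SAP rule move a switched participant?** The misallocation text in SAP Section 6.4 moves a placebo participant to a spesolimab safety group only if at least one vial of spesolimab was received before Week 16. The planned switch at Week 16 moves nobody. Combined with the Day 1 rule and the definition of the total-spesolimab group, events after the switch are placebo events in the SAP.

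**2. Does working by period cure it?** No. Maintenance period III starts at the Week 16 dose, so its placebo column would consist entirely of spesolimab time.

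**3. Share of visits.** Treatment runs from Visit 2 to Visit 31, which is 30 visits. Visits 14 to 31 are 18, and 18/30 = 60%.

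**4. Share of time (assumed; treatment length is redacted).**
- Visit 10 is Week 8 (SAP 7.4.1) and Visit 14 is Week 16 (SAP 6.1), so the spacing is (16 − 8)/(14 − 10) = 2 weeks.
- If that spacing continues, Visit 31 = 16 + 17 × 2 = Week 50.
- Protocol Section 6 places the end-of-study visit 112 days after the last dose or 98 days after EoT, so EoT is 112 − 98 = 14 days after the last dose: Week 52.
- Check: Visit 19 = 16 + 5 × 2 = Week 26, which fits the South African tuberculosis test required there at about 6 months.
- Rolling over at Week 52: 52 − 16 = 36 spesolimab weeks of 52 (69%).
- Followed through the 16-week residual period after Week 50: 66 − 16 = 50 of 66 weeks (76%).

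**5. Effect on a rate ratio (illustration).** The documents give no AE rates. Assume constant rates, a true spesolimab-to-placebo ratio RR = 2, p = 16 placebo weeks and a spesolimab weeks in the placebo record. Counting all events:

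apparent RR = RR / [(p + a × RR)/(p + a)]

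| Weeks in placebo record (p + a) | Share after switch | Apparent RR |
|---|---|---|
| 24 | 33% | 1.50 |
| 32 | 50% | 1.33 |
| 48 | 67% | 1.20 |
| 52 | 69% | 1.18 |
| 64 | 75% | 1.14 |
| 66 | 76% | 1.14 |

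For 52 weeks: 2/[(16 + 72)/52] = 2/1.692 = 1.18.

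**6. The SAP's own rate (Section 7.8.1)** counts first events and stops time at risk at onset. With placebo hazard λ per year, 2λ after the switch, and times in years:
- S = exp(−λp)
- events = 1 − S·exp(−2λa)
- time at risk = (1 − S)/λ + S·[1 − exp(−2λa)]/(2λ)
- apparent RR = 2λ/(events/time at risk)

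For λ = 0.5 and 52 weeks: p = 16/52 = 0.308 and a = 36/52 = 0.692, so S = 0.857, events = 0.571, time at risk = 0.714 and rate = 0.800. Apparent RR = 1.0/0.800 = 1.25.

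| Placebo rate per 100 patient-years | 52 weeks | 66 weeks |
|---|---|---|
| 2 | 1.18 | 1.14 |
| 50 | 1.25 | 1.21 |
| 100 | 1.32 | 1.30 |

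Under these assumptions, attribution by treatment at onset returns the true ratio of 2.0.

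**The case against.** The strongest reply is that the SAP is ambiguous rather than wrong. Section 7.8.1 speaks of actual treatment received without a Day 1 limit. Section 6.7 sorts AE tables by onset date. Section 7.8.1 also defers summarisation details to a company standard that is not available here. Since Section 4 lists no change, the protocol's rule might be said still to govern. In addition, part of the label list in Section 6.1 is redacted, including the placebo label.

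None of this removes the problem. Sorting by date does not choose a treatment column. The looser wording in 7.8.1 does not say at onset, and the set that governs all safety analyses is defined by Day 1. A redacted label cannot alter an unredacted Day 1 rule. If the SAP can be read both ways, it still needs correcting.

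Some points stand:
- By-visit displays of vital signs and local tolerability do not mix periods. After Week 16 they are mislabelled rather than blended; the mixing is confined to pooled summaries and last, minimum and maximum values.
- SAP Section 7.7 summarises dose and exposure by stage, so spesolimab exposure in the placebo-randomised group stays visible there, although their adverse events are not separated.
- Visit spacing is not constant: Visits 2 to 10 cover 8 weeks in 8 intervals. Nothing visible confirms 2-week spacing after Visit 19, so Week 52 remains an assumption.
- Treatment at onset also raises the low-dose participants who may be up-titrated from Visit 14 and any regimen adapted from Visit 23. The SAP should say how both are labelled.

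**Conclusion.** The concern holds. Followed as written, the SAP counts spesolimab events and person-time after Week 16 under placebo and omits them from the total-spesolimab column. That contradicts the protocol's stated rule without being declared.

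The 60% share of treatment visits comes directly from the visit schedule, but it is not a share of person-time. The time shares of 69% and 76% rest on the assumed 52-week schedule. The apparent ratios of 1.18 and 1.14 for a true 2.0 also assume constant rates and a chosen true ratio. The direction is the same for every duration shown; the size is not known. Spesolimab makes up more than half of the placebo record in a completing participant whenever that record exceeds 32 weeks.

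The consequence is bounded. The Week 8 and Week 16 AE tables, which bear on the Part 2 dose decision, precede the switch, as do the laboratory summaries to Week 16. This should be corrected before the whole-period outputs are produced, but it does not threaten the primary analysis.

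**What to change.** - **Keep** the tables up to Week 16 as the placebo-versus-spesolimab comparison, and state the same cut for vital signs and local tolerability.
- **Amend SAP 6.1, 6.4 and 7.8** to treatment at onset for whole-period outputs. Placebo events and time at risk end at the first spesolimab dose. Data after the switch go to a separate placebo-to-spesolimab column and to an all-spesolimab-exposure column.
- **Add a rule for the switch day.** SAP Section 7.8 notes that AE onset time is not collected. One workable rule is to count AEs starting that day under spesolimab in every table.
- **State the labelling** of low-dose participants up-titrated from Visit 14 and of any regimen adapted from Visit 23.
- **If Day 1 grouping is intended**, declare the departure from Protocol 7.2.6 in SAP Section 4 and label the column as placebo followed by spesolimab.

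The cost is SAP wording and two extra columns in the whole-period tables. Dosing dates are already collected, so no new data are needed.
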